6.5 Dose escalation and dose modification

Investigational or other study treatment dose adjustments and/or interruptions are not permitted.

6.5.1 Dose modifications

Dose adjustments and/or interruptions of a subject's study treatment are not permitted.

The discontinuation of study treatment rules (Section 9.1.1) must be adhered to if a subject cannot complete inhalation of the required capsules per the study protocol.

Any dose interruption must be recorded on the Dosage Administration Record CRF.

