- Call the patient promptly when any one specific alert type (e.g. PEF<60%) is received on consecutive days to further assess the clinical status. This may include urgent clinic visits as appropriate and/or immediate treatment.
- Implement prompt treatment as necessary
- Report all types of events in the CRF

If patients believe their symptoms are worsening and/or receive alerts as outlined above, the patient should also notify the investigator and be evaluated by the investigator and treated as clinically appropriate.

Investigator and the site study team must check and encourage patients' compliance with study medications and the eDiary/ePEF device. Should there be any compliance issue on study drug or e-diary completion potentially putting the patient's safety at risk, Investigator must consider temporary or permanent discontinuation of study drug.

Worsening of asthma symptoms may require unscheduled evaluation between visits. Study site personnel must be available to monitor and document the patient's progress until the asthma worsening has resolved.

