A positive urine test requires interruption of study treatment until serum test is done. If the serum test is negative, study treatment should continue.

The patient must be followed to understand the outcome of the pregnancy.

If the result of urine pregnancy test at the end of run-in visit is positive, the patient must not be randomized until the results is confirmed by a serum pregnancy test.

Assessments of Fertility

Medical documentation of oophorectomy, hysterectomy, or bilateral tubal ligation must be retained as source documents. Subsequent hormone level assessment to confirm the woman is not of child-bearing potential must also be available as source documentation in the following cases:

- Surgical bilateral oophorectomy without a hysterectomy
- Reported 12 months of natural (spontaneous) amenorrhea with an appropriate clinical profile.

In the absence of the above medical documentation, FSH (Follicle Stimulating Hormone) testing is required of any female subject regardless of reported reproductive/menopausal status at screening/baseline.

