10.2 Additional Safety Monitoring

10.2.1 Liver safety monitoring

To ensure subject safety and enhance reliability in determining the hepatotoxic potential of an investigational drug, a standardized process for identification, monitoring and evaluation of liver events has to be followed.

The following two categories of abnormalities / adverse events have to be considered during the course of the study (irrespective of whether classified/reported as AE/SAE):

- Liver laboratory triggers, which will require repeated assessments of the abnormal laboratory parameter
- Liver events, which will require close observation, follow-up monitoring and contributing factors are recorded on the appropriate CRFs

Please refer to Section 16.2 for complete definitions of liver laboratory triggers and liver events.

Every liver event defined in Table 16-1 should be followed up by the investigator or designated personnel at the trial site, as summarized below. Additional details on actions required in case of liver events are outlined in Table 16-2. Repeat liver chemistry tests (i.e. ALT, AST, TBL, PT/INR, ALP and GGT) to confirm elevation.

- These liver chemistry repeats will be performed using the central laboratory. If results will not be available from the central laboratory, then the repeats can also be performed at a local laboratory to monitor the safety of the subject. If a liver event is subsequently reported, any local liver chemistry tests previously conducted that are associated with this event should have results recorded on the appropriate CRF.
- If the initial elevation is confirmed, close observation of the subject will be initiated, including consideration of treatment interruption if deemed appropriate.
- Discontinuation of the investigational drug (refer to the Discontinuation of study treatment Section 9.1.1), if appropriate
- Hospitalization of the subject if appropriate
- Causality assessment of the liver event
- Thorough follow-up of the liver event should include investigations (can include based on investigator's discretion): serology tests, imaging and pathology assessments,

hepatologist's consultancy; obtaining more detailed history of symptoms and prior or concurrent diseases, history of concomitant drug use, exclusion of underlying liver disease

All follow-up information and procedures performed must be recorded as appropriate in the CRF.

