	 If elevation persists for more than 2 weeks, discontinue the study drug 	
	Establish causality	
	 Record the AE and contributing factors (e.g. conmeds, med hx, lab) in the appropriate CRF 	
> 3 × ULN accompanied by symptoms ^b	• Discontinue the study treatment immediately	ALT, AST, TBL, Alb, PT/INR, ALP and GGT until resolution ^c
	 Hospitalize if clinically appropriate 	(frequency at investigator discretion)
	Establish causality	
	 Record the AE and contributing factors (e.g. conmeds, med hx, lab) in the appropriate CRF 	
> 3 to ≤ 5 × ULN (patient is asymptomatic)	 Repeat LFT within the next week 	Investigator discretion Monitor LFT within 1 to 4
	 If elevation is confirmed, initiate close observation of the patient 	weeks
ALP (isolated)		
> 2 × ULN (in the absence of known bone pathology)	 Repeat LFT within 48 hours 	Investigator discretion Monitor LFT within 1 to 4
	 If elevation persists, establish causality 	weeks or at next visit

Criteria	Actions required	Follow-up monitoring	
	 Record the AE and contributing factors (e.g. conmeds, med hx, lab) in the appropriate CRF 		
TBL (isolated)			
> 2 × ULN (in the absence of known Gilbert syndrome)	 Repeat LFT within 48 hours 	ALT, AST, TBL, Alb, PT/INR, ALP and GGT until resolution ^c (frequency at investigator	
	 If elevation persists, discontinue the study drug immediately 	discretion) Test for hemolysis (e.g.	
	Hospitalize if clinically appropriate	reticulocytes, naptoglobin, unconjugated [indirect] bilirubin)	
	 Establish causality 		
	 Record the AE and contributing factors (e.g. conmeds, med hx, lab) in the appropriate CRF 		
> 1.5 to ≤ 2 × ULN (patient is asymptomatic)	 Repeat LFT within the next week 	Investigator discretion Monitor LFT within 1 to 4	
	 If elevation is confirmed, initiate close observation of the patient 	weeks or at next visit	
Jaundice	 Discontinue the study treatment immediately 	ALT, AST, TBL, Alb, PT/INR, ALP and GGT until resolution ^c	
	 Hospitalize the patient 	(frequency at investigator discretion)	
	 Establish causality 		
	 Record the AE and contributing factors (e.g. conmeds, med hx, lab) in the appropriate CRF 		
Any AE potentially indicative of a liver toxicity*	 Consider study treatment interruption or discontinuation 	Investigator discretion	
	 Hospitalization if clinically appropriate 		
	 Establish causality 		
	 Record the AE and contributing factors (e.g. conmeds, med hx, lab) in the appropriate CRF 		

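### The protocol bars every interruption of study treatment, yet requires one after a positive urine pregnancy test; the sections on liver findings, adverse events and compliance also contemplate one

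*Protocol*

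**What the plan says.** The prohibition appears twice. Protocol Section 6.5 reads "Investigational or other study treatment dose adjustments and/or interruptions are not permitted", and Section 6.5.1 reads "Dose adjustments and/or interruptions of a subject's study treatment are not permitted". Neither section names an exception or points to one elsewhere. Section 6.5.1 adds "Any dose interruption must be recorded on the Dosage Administration Record CRF", and Section 6.6.1 also has interruptions collected on the eCRF.

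Five other parts of the protocol provide for an interruption:

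- Section 8.5.3 (pregnancy): "A positive urine test requires interruption of study treatment until serum test is done", followed by "If the serum test is negative, study treatment should continue".
- Section 8.5, on home urine kits when a public health emergency prevents a site visit: the participant tests first and takes study treatment only if the result is negative.
- Section 8.4.3.4, for compliance problems that could endanger the patient: "Investigator must consider temporary or permanent discontinuation of study drug".
- Section 10.2.1, for a confirmed liver test elevation: close observation, "including consideration of treatment interruption if deemed appropriate". Table 16-2, for adverse events suggesting liver toxicity: "Consider study treatment interruption or discontinuation".
- Section 10.1.1: interrupting or withdrawing investigational treatment is one of the listed responses to an adverse event.

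For the analysis, SAP 2.1.1.3 and 2.5.3 (and Protocol 12.4.3) count efficacy values as on-treatment from the first double-blind dose to 1 day after the last. They have no rule for a gap between those dates.

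**The concern.** A prohibition without exception and a mandatory interruption cannot both be followed. The situation concerned is a possible pregnancy, where a site should not have to choose between two sections. A site that follows Section 8.5.3 departs from 6.5.1 as written, and could have this recorded under the treatment-deviation category listed in SAP 2.3.1.

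There is also a consequence for the data. The primary estimand is the effect had every patient stayed on assigned treatment for 12 weeks. If a patient pauses and resumes, an FEV1 taken off drug during the pause enters the primary analysis as an on-drug value.

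**Working it through.** The main point is a comparison of text. The documents give no figure to reproduce.

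**Step 1. How each provision stands against 6.5 and 6.5.1.**

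| Provision | Force | Permanent stop also offered? | Can a site satisfy both? |
|---|---|---|---|
| 8.5.3, positive urine test | Required; dosing continues if serum is negative | No, only after a positive serum test | No |
| 8.5, home urine kit | Dosing held unless negative | No | No, if the test is positive |
| 8.4.3.4, compliance | Must be considered | Yes | Yes |
| 10.2.1, liver elevation | To be considered | Yes, in the next bullet | Yes |
| Table 16-2, liver adverse event | To be considered | Yes | Yes |
| 10.1.1, adverse events | Listed option | Yes | Yes |

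The strict conflict is therefore the urine-test rule, in its two settings. The other four provisions assume an option that 6.5.1 removes. The Table 16-2 rows that call only for discontinuation do not conflict with 6.5.1.

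**Step 2. When the urine-test rule can apply during randomized dosing.** Table 8-1 schedules urine tests at run-in, end of run-in, Week 16 and Week 20. At end of run-in, 8.5.3 has its own hold on randomization. Weeks 16 and 20 are in the drug-free follow-up. Weeks 4, 8 and 12 use serum tests, and a positive serum test leads to discontinuation, which fits 6.5.1. What remains is home kits in a public health emergency and unscheduled urine tests. Of the on-drug visits, Table 8-1 marks only Weeks 2 and 4 for off-site assessments, and of these only Week 4 has a pregnancy test.

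**Step 3. The on-treatment window.** As an illustration, suppose a patient doses to Day 50, pauses, and has the Week 8 visit on Day 57.

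- Dosing never resumes: the window closes on Day 50 + 1 = Day 51, so the Day 57 value is excluded.
- Dosing resumes on Day 60: the last dose is now after Day 57, so the Day 57 value is kept as on-treatment.

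The same measurement, 57 − 50 = 7 days after the most recent dose, is handled in opposite ways depending on a later event.

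**Step 4. Possible size.** The documents give no frequency. Assume that a fraction *p* of an active arm has one of the two endpoint visits inside such a gap. Assume also, as an upper bound, that the whole planning effect of 0.120 L is lost at that visit. With complete data, the endpoint averages two visits, so each such patient's average falls by 0.120 / 2 = 0.060 L, and the arm mean falls by *p* × 0.060 L. For *p* = 1% this is 0.0006 L (0.6 mL). For *p* = 5% it is 0.003 L (3 mL), or 3 / 120 = 2.5% of the planning effect. The range for *p* is an assumption made here.

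**The case against.** The strongest reply is that the protocol plainly expects interruptions. It tells sites to record them in 6.5.1 and 6.6.1, and 6.5.1 can be read as barring only elective changes. Section 14.1 also expects investigators to take immediate safety action even where that departs from the protocol, and Section 9.1.1 requires treatment to stop in any situation posing a safety risk. A reader might infer from the clash that sites are bound to keep dosing through a possible pregnancy or a liver signal. The documents do not support that, because these two sections prevent it.

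This part of the reply stands, but it does not remove the contradiction. Recording an event is not permission for it, and no section limits 6.5.1 to elective changes. Section 14.1 allows the action only as a deviation. Section 9.1.1 leads to stopping treatment, whereas 8.5.3 describes a pause with possible resumption.

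It is also fair to object that the provisions in 8.4.3.4, 10.1.1, 10.2.1 and Table 16-2 do not make compliance impossible, and that the mandatory conflict seldom arises on drug. Both objections are accepted. Finally, the SAP reports early termination with 335 patients enrolled, so amended site instructions have limited reach in this trial.

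**Conclusion.** The inconsistency is real and in the current text. Sections 6.5 and 6.5.1 cannot be followed together with 8.5.3, or with the home-testing rule in 8.5 when the test is positive. The compliance, liver and adverse-event provisions are inconsistent with 6.5.1 in a weaker sense. During randomized dosing the mandatory conflict is likely to be rare. That judgement rests on the visit schedule, since the documents give no count of positive urine tests, home tests or interruptions.

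The point about the analysis is secondary. A reader might infer that the primary result is materially biased, but the documents give no frequency or effect to show that, and under the assumptions above the dilution is a few millilitres at most. What stands is a mismatch between the on-treatment definition and the estimand. It occurs only when dosing stops, later resumes, and the gap covers an FEV1 visit.

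**What to change.** **Protocol.** The sponsor should reconcile 6.5 and 6.5.1 with 8.5, 8.5.3, 8.4.3.4, 10.1.1, 10.2.1 and Table 16-2, so that one rule on interruption applies throughout. This review takes no position on what that rule should be. The cost is a wording clarification.

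**SAP.** Add a sentence to 2.1.1.3: for the primary analysis, FEV1 recorded more than 1 day into a documented interruption is off-treatment and set to missing. This applies to gaps the same 1-day margin that already applies after the last dose, and the MMRM then handles the value under its missing-at-random assumption. The sentence should define a documented interruption from the existing eCRF record. It should also say whether it covers the secondary endpoints, which use the same on-treatment definition. No new data are needed, and the downside is the loss of a few observations.

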6.5.2 Follow-up for toxicities

Not applicable.

6.5.2.1 Follow up on potential drug-induced liver injury (DILI) cases

Subjects with transaminase increase combined with total bilirubin (TBL) increase may be indicative of potential DILI and should be considered as clinically important events.

The threshold for potential DILI may depend on the subject's baseline AST/ALT and TBL value; subjects meeting any of the following criteria will require further follow-up as outlined below:

- For subjects with normal ALT and AST and TBL value at baseline: AST or ALT > 3.0 x ULN combined with TBL > 2.0 x ULN
- For subjects with elevated AST or ALT or TBL value at baseline: [AST or ALT > 2 x baseline AND > 3.0 x ULN] OR [AST or ALT > 8.0 x ULN], combined with [TBL > 2 x baseline AND > 2.0 x ULN]

Medical review needs to ensure that liver test elevations are not caused by cholestasis, defined as ALP elevation > 2.0 x ULN with R value < 2 in subjects without bone metastasis, or elevation of ALP liver fraction in subjects with bone metastasis.

Note: The R value is calculated by dividing the ALT by the ALP, using multiples of the ULN for both values. It denotes whether the relative pattern of ALT and/or ALP elevation is due to cholestatic ($R \le 2$), hepatocellular ($R \ge 5$), or mixed (R > 2 and < 5) liver injury.

In the absence of cholestasis, these subjects should be immediately discontinued from study treatment, and repeat Liver function test (LFT) testing as soon as possible, preferably within 48 hours from the awareness of the abnormal results. The evaluation should include laboratory tests, detailed history, physical assessment, and the possibility of liver metastasis or new liver lesions, obstructions/compressions, etc.

1. Laboratory tests should include ALT, AST, albumin, creatine kinase, total bilirubin, direct and indirect bilirubin, GGT, prothrombin time (PT)/INR, and alkaline phosphatase.

2. A detailed history, including relevant information, such as review of ethanol, concomitant medications, herbal remedies, supplement consumption, and history of any pre-existing liver conditions or risk factors, should be collected.

3. Further testing for acute hepatitis A, B, C or E infection and liver imaging (e.g. biliary tract) may be warranted.

4. Obtain PK sample, as close as possible to last dose of study drug, if PK analysis is performed in the study.

5. Additional testing for other hepatotropic viral infection (CMV, EBV or HSV), autoimmune hepatitis or liver biopsy may be considered as clinically indicated or after consultation with specialist/hepatologist.

All cases confirmed on repeat testing meeting the laboratory criteria defined above, with no other alternative cause for LFT abnormalities identified, should be considered as "medically significant," and thus, meet the definition of SAE and should be reported as SAE using the term "potential drug-induced liver injury." All events should be followed up with the outcome clearly documented.

Please refer to Section 16.2 for complete definitions of liver laboratory triggers and liver events.

Every liver event defined in Table 16-1 should be followed up by the investigator or designated personnel at the trial site. Additional details on actions required in case of liver events are outlined in Table 16-2.

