16.2 Liver event and Laboratory trigger Definitions and Follow-up Requirements

	Definition/ threshold	
LIVER LABORATORY TRIGGERS	• $3 \times ULN < ALT / AST \le 5 \times ULN$	
	• 1.5 x ULN < TBL ≤ 2 x ULN	
LIVER EVENTS	• ALT or AST > 5 × ULN	
	 ALP > 2 × ULN (in the absence of known bone pathology) 	
	 TBL > 2 × ULN (in the absence of known Gilbert syndrome) 	
	• ALT or AST > 3 × ULN and INR > 1.5	
	 Potential Hy's Law cases (defined as ALT or AST > 3 × ULN and TBL > 2 × ULN [mainly conjugated fraction] without notable increase in ALP to > 2 × ULN) 	
	 Any clinical event of jaundice (or equivalent term) 	
	 ALT or AST > 3 × ULN accompanied by (general) malaise, fatigue, abdominal pain, nausea, or vomiting, or rash with eosinophilia 	
	 Any adverse event potentially indicative of a liver toxicity* 	

*These events cover the following: Hepatic failure, fibrosis and cirrhosis, and other liver damagerelated conditions; the non-infectious hepatitis; the benign, malignant and unspecified liver neoplasms TBL: total bilirubin; ULN: upper limit of normal

Table 16-2	Follow up rec	uirements for	liver events and	I laboratory triggers

Criteria	Actions required	Follow-up monitoring
Potential Hy's Law case ^a	 Discontinue the study treatment immediately 	ALT, AST, TBL, Alb, PT/INR, ALP and GGT until resolution
	 Hospitalize, if clinically appropriate 	discretion)
	 Establish causality 	
	 Record the AE and contributing factors (e.g. conmeds, med hx, lab) in the appropriate CRF 	
ALT or AST		
> 8 × ULN	 Discontinue the study treatment immediately 	ALT, AST, TBL, Alb, PT/INR, ALP and GGT until resolution ^c (frequency at investigator discretion)
	 Hospitalize if clinically appropriate 	
	 Establish causality 	

Table 16-1 Liver event and laboratory trigger definitions

Criteria	Actions required	Follow-up monitoring
	 Record the AE and contributing factors (e.g. conmeds, med hx, lab) in the appropriate CRF 	
> 3 × ULN and INR > 1.5	 Discontinue the study treatment immediately 	ALT, AST, TBL, Alb, PT/INR, ALP and GGT until resolution ^c
	 Hospitalize, if clinically appropriate 	discretion)
	Establish causality	
	 Record the AE and contributing factors (e.g. conmeds, med hx, lab) in the appropriate CRF 	
> 5 to ≤ 8 × ULN	 Repeat LFT within 48 hours 	ALT, AST, TBL, Alb, PT/INR, ALP and GGT until resolution ^c
	 If elevation persists, continue follow-up monitoring 	(frequency at investigator discretion)

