^a Elevated ALT/AST > 3 × ULN and TBL > 2 × ULN but without notable increase in ALP to > 2 × ULN ^b (General) malaise, fatigue, abdominal pain, nausea, or vomiting, or rash with eosinophilia ^c Resolution is defined as an outcome of one of the following: (1) return to baseline values, (2) stable values at three subsequent monitoring visits at least 2 weeks apart, (3) remain at elevated level			

after a maximum of 6 months, (4) liver transplantation, and (5) death.

Based on investigator's discretion investigation(s) for contributing factors for the liver event can include: Serology tests, imaging and pathology assessments, hepatologist's consultancy; obtaining more detailed history of symptoms and prior or concurrent diseases, history of concomitant drug use, exclusion of underlying liver disease.

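### A mixed-pattern liver injury that Section 6.5.2.1 stops at once has no immediate-stop row in Table 16-2, which on the ordinary reading delays the stop by about 48 hours

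*Protocol*

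**What the plan says.** **Protocol Section 6.5.2.1.** With normal baseline values, ALT or AST > 3 x ULN together with TBL > 2 x ULN is potential drug-induced liver injury (DILI). Medical review must first rule out cholestasis, "defined as ALP elevation > 2.0 x ULN with R value < 2 in subjects without bone metastasis". R is ALT divided by ALP, each as a multiple of its ULN, and the note names a separate category, "mixed (R > 2 and < 5) liver injury". The action is: "In the absence of cholestasis, these subjects should be immediately discontinued from study treatment". Repeat testing follows the stop. The section then points onward: "Additional details on actions required in case of liver events are outlined in Table 16-2". Section 10.2.1 makes the same referral without going through 6.5.2.1.

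**Protocol Section 16.2.** Table 16-1 limits potential Hy's Law to ALT or AST > 3 x ULN with "TBL > 2 × ULN [mainly conjugated fraction] without notable increase in ALP to > 2 × ULN", and footnote a to Table 16-2 repeats the limit ("but without notable increase in ALP to > 2 × ULN"). The rows of Table 16-2 fall into three groups:

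- **Immediate stop:** potential Hy's Law; ALT or AST > 8 x ULN; ALT or AST > 3 x ULN with INR > 1.5; ALT or AST > 3 x ULN with listed symptoms; jaundice.
- **Repeat test first:** ALT or AST > 5 to 8 x ULN ("If elevation persists for more than 2 weeks, discontinue the study drug"); ALT or AST > 3 to 5 x ULN without symptoms ("Repeat LFT within the next week", then close observation if confirmed); TBL > 2 x ULN (repeat within 48 hours, stop if it persists); ALP > 2 x ULN (repeat within 48 hours, no stop action). The TBL and ALP rows are both headed as isolated elevations.
- **Discretionary:** a catch-all row for adverse events that suggest liver toxicity, which asks the site to consider interrupting or discontinuing.

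Neither section says which rule governs when they differ.

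**The concern.** Section 6.5.2.1 exempts a patient from the immediate stop only if ALP is raised **and** R is low. The Hy's Law row drops a patient as soon as ALP is raised, whatever R is. A mixed-pattern case (raised ALP, R above 2) is therefore to be stopped under the body text but meets no immediate-stop row in the table.

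The stake is patient safety. Transaminases and bilirubin rising together is the pattern that 6.5.2.1 treats as potential DILI, and the drug is taken daily. A site that reaches Table 16-2 from Section 10.2.1 may never see the 6.5.2.1 instruction and could wait for a repeat result before stopping. Sections 6.5 and 6.5.1 do not permit dose interruptions, while Section 10.2.1 mentions considering one, so such a site also has no clear instruction to hold the dose in the meantime.

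**Working it through.** The plan gives no figure to reproduce here. The check compares two sets of rules. All laboratory values are multiples of ULN, baseline is normal, and there are no listed symptoms, no jaundice and INR ≤ 1.5.

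**Inputs**

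- Section 6.5.2.1: stop if (ALT or AST > 3) and TBL > 2, unless ALP > 2 and R < 2, where R = ALT/ALP.
- Section 16.2: with INR, symptoms and jaundice set aside, the immediate-stop rows left are Hy's Law (ALT or AST > 3, TBL > 2, ALP not > 2) and ALT or AST > 8.
- Section 6.1.4: 84 planned treatment days, one dose a day.

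**Bounds of the gap.** The Hy's Law row is escaped only if ALP > 2. The cholestasis exemption is clearly escaped if R > 2, so ALT > 2 x 2 = 4. The > 8 row is escaped if ALT and AST are ≤ 8. Then ALP < 8/2 = 4, and R < 8/2 = 4, which lies inside the mixed range.

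**Worked cases (AST = ALT)**

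| Case | ALT | ALP | TBL | R = ALT/ALP | 6.5.2.1 | Table 16-2 immediate-stop row |
|---|---|---|---|---|---|---|
| A | 4.5 | 2.1 | 2.3 | 2.14 | stop now | none |
| B | 6 | 2.2 | 2.5 | 2.73 | stop now | none |
| C | 6 | 3.2 | 2.5 | 1.88 | exempt | none |

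A and B fall in the gap. C does not, because neither text stops it at once.

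**Grid check.** Both rules were evaluated over ALT (= AST) 0.5 to 12 and ALP 0.5 to 6 in steps of 0.1, at TBL 1.5, 2.1, 3 and 5. Section 6.5.2.1 stops 9,120 of these points. Of those, 1,200 meet no immediate-stop row, all with ALT 4.2 to 8.0, ALP 2.1 to 4.0 and R 2.0 to 3.8. Points at ALP = 4.0 arise only at R = 2 exactly, which the definition (R < 2) does not exempt. Setting INR to 1.6, or adding symptoms or jaundice, reduces the 1,200 to 0. These counts confirm the shape of the region. They are not patient frequencies.

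**Size of the delay under Table 16-2 alone**

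- *Ordinary reading.* TBL > 2 x ULN is a liver event in Table 16-1 with no requirement that it be isolated, so its Table 16-2 row is applied. A and B are repeated within 48 hours and stopped if confirmed: about 2 doses, 2/84 = 2.4% of planned days. This assumes the result is available by then; the protocol gives no turnaround time.
- *Literal reading of the isolated heading.* The TBL row drops out. A is repeated within a week (up to 7 doses, 7/84 = 8.3%) with no stop action in its row. B stops only after more than 2 weeks (more than 14 doses, over 14/84 = 16.7%).

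**The case against.** The strongest reply is that a careful site would stop anyway.

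- Section 6.5.2.1 applies at every site, no table row forbids stopping, and the referral presents Table 16-2 as adding detail to the instruction just given.
- The catch-all liver-toxicity row invites discontinuation without waiting for a repeat test.
- Section 9.1.1 uses *must* for any safety risk to the subject, a stronger verb than the *should* in 6.5.2.1.
- Section 10.2.1 raises treatment interruption once an elevation is confirmed.
- The region needs many conditions at once, and screening already excludes hepatic disease and lists transaminases above 2 x ULN and bilirubin above 1.3 x ULN as excluding abnormalities.

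Most of this stands, and it limits the point. A reader might infer that the table offers nothing but repeat tests for this patient. The catch-all row shows otherwise, although it is discretionary and depends on the case being recorded as an adverse event. A reader might also infer a delay of one to more than two weeks. That needs the literal reading of *isolated*, which would leave a bilirubin event defined in Table 16-1 with no bilirubin action at all, so it should not be taken as the expected delay.

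What the reply does not remove is that the catch-all row, 9.1.1 and 10.2.1 all depend on the investigator recognising the case, whereas 6.5.2.1 sets numerical criteria and an immediate action. A site sent to the table from 10.2.1 finds no row carrying that action.

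**Conclusion.** The point holds as a gap in the action table. For an asymptomatic, non-jaundiced patient with normal baseline values, INR ≤ 1.5, ALT > 4 to 8, ALP > 2 to < 4 and TBL > 2 (all x ULN) and R > 2, Section 6.5.2.1 says treatment should stop immediately and no Table 16-2 row orders it. AST is assumed to be no more than 8 x ULN. On the ordinary reading the delay is about 48 hours.

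A reader might go further and conclude that the protocol gives incompatible orders. It does not, because stopping complies with both texts. Nor is there any consequence for the planned safety tables: SAP Section 5.3 counts ALT or AST > 3 x ULN with bilirubin > 2 x ULN without an ALP limit, as well as the Hy's Law subset.

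The documents give no frequency for this pattern. SAP Section 1.1 records early termination with 335 enrolled, so the benefit is to patients still dosing and to any protocol that reuses the text. The correction is worth making because it is cheap and concerns a stopping rule.

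**What to change.** 1. **Add a row to Table 16-2:** *Potential DILI under Section 6.5.2.1, not cholestatic (that is, not both ALP > 2 x ULN and R < 2): stop study treatment at once, then repeat liver tests promptly, with 48 hours as the target.* Leave the Hy's Law definition and footnote a unchanged.
2. **Add a sentence to Sections 6.5.2.1 and 16.2:** *Study treatment stops at once if either the Section 6.5.2.1 criteria or any immediate-discontinuation row of Table 16-2 is met.* This also settles the reverse case. With baseline ALT 1.9 rising to 3.5, TBL 2.3 and normal ALP (all x ULN), and AST no higher than ALT at each time, the Hy's Law row stops the patient. Section 6.5.2.1 does not, because 3.5 is below 2 x 1.9 = 3.8.
3. **Optional tidy-up:** Section 6.5.2.1 defines cholestasis by R < 2 but its note uses R ≤ 2. Use one convention in both places.

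The cost is a protocol wording amendment and possibly a few more discontinuations in mixed-pattern cases. No extra tests, patients or SAP changes are needed.
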